During the recruitment telephone call, interested individuals will be asked questions to confirm eligibility, to determine their access to and facility with technological devices, and the extent to which they can access broadband internet. Should the participant need a device to participate in the visits described in this protocol, the study team will send a device with Wi-Fi and cellular data capabilities for participants' temporary use. Eligible participants will be consented orally, assigned Outcome Measure surveys, and then assigned to a study arm (*see randomization section below*). Participants assigned to the Intervention arm will be scheduled additional visits with a Pain Care Manager (PCM) and Community Health Worker (CHW). Interested individuals will not be assigned to an arm until their Outcome Measure surveys are completed. This same Outcome Measure survey bundle will be assigned to enrolled participants either on paper or electronically at 3 months and 6 months post enrollment. Enrolled participants will be mailed a copy of the oral consent so the discussed details and team contact information is readily available to them.

We are seeking a waiver of signed informed consent as well as a waiver of signed HIPAA for this protocol. Due to the minimal risk posed by this study, as well as the complexities of recruiting rural and Hispanic populations and the likelihood of including undocumented Hispanic participants, we believe that a waiver is justified and consistent with the intent of existing regulations.

Randomization

This will be a two-arm, parallel group randomized clinical trial. Research coordinators will register participants

on a password protected MC Cancer Center remote registration/randomization application. Randomization will use a dynamic allocation procedure that balances the marginal distributions of the stratification factors per Pocock-Simon randomization method.¹ Stratification factors will include cancer stage, rural residence, MC HCS site, and Hispanic ethnicity.

The participants randomized into the control group will receive enhanced usual care which will include access to the educational and pain self-management materials developed for the ASCENT trial. Those randomized into the intervention will follow the process outlined in the “Intervention” section of this protocol.

Remuneration

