Also included in this aim are interviews or focus groups with the study interventionists (PCMs & CHWs). We provided extensive training to the ASCENT CHWs and PCMs, discussed role delineation between the PCM and CHW roles, provided role playing opportunities, and held weekly touchpoints with the PCM and CHW interventionists. However, opportunities remain to further refine the CHW role in the context of the ASCENT intervention and identify additional training needs. To study this, we will hold quarterly-biannual focus group/debriefings with interventionists (e.g., CHWs, PCMs) to understand their needs for additional role clarification, training, and ongoing challenges. There will be no compensation for participating in these focus groups/interviews, interested team members will be given a consent document and the option to decline. The debriefings will be recorded for transcription and data analysis purposes.

Control Condition

Patients randomized to usual care group will be administered trial PROM outcomes. Their scores will be viewable

in the EHR by their care teams. Patients will be encouraged to discuss moderate or severe pain with their care teams and to track their pain via print log or portal. In addition, control group participants will be provided access to the ASCENT multi-modal pain management materials and self-management instruction. A few materials (pain log, general pain education material and wifi guide, etc) will be included in their study post randomization/welcome mailing. Other than this, there will be no attempt by study personnel to influence pain management. While randomization by patient means oncologists will have both intervention and control patients in their practices, numerous effectiveness trials of collaborative care for symptom management by us as well as others have shown there is little spillover of the intervention to usual care patients in the absence of the care management, symptom monitoring and treatment adjustment that occurs with enhanced care of varying types.²⁻⁶ Any minor spillover that does occur results in a conservative estimate of the intervention's effectiveness.

Intervention Fidelity

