Mediators Will include self-efficacy for managing symptoms (PROMIS SF 4a), adherence to behavioral MMPC plan components (logged count data), use of ASCENT e-tools (minutes/week), social isolation (PROMIS SF 4a), informational support (PROMIS SF 4a), and opioid consumption in oral morphine equivalents (OMEs) collected via EHR prescriptions.

Health care utilization Healthcare utilization for ASCENT will consider hospitalizations and ED visits which will be ascertained using EHR entries and administrative billing data. Data collected for hospitalizations will include admission and discharge diagnoses, length of stay, whether an admission was planned for anti-cancer treatment or unplanned. The majority, but not all, of patients’ health care utilization will occur at MC facilities. Established patterns suggest that 80% of patients care will occur at an MC facility. However, we will use imputation methods and sensitivity analyses to assess the impact of mis-ascertainment of utilization data.

Measure	Domain	Items	Time min.	HEAL data	Collected 0,3,6 mo.
Primary					
BPI SF	Pain	7	3	✓	✓
Secondary					
PROMIS SF	Physical Function	4	2	✓	✓
EQ-5D-3L	QoL	5	2.5		✓
PHQ-2	Depression	2	2	✓	✓
GAD-2	Anxiety	2	1	✓	✓
PROMIS SF	Sleep	6	3	✓	✓
Mediators					
PROMIS SF	Self-efficacy	4	2		✓
PROMIS SF	Social isolation	4	2		✓
PROMIS SF	Informational support	4	2		✓

Risks and Benefits

The risks of the ASCENT trial study are minimal as participants are being potentially offered additional support and expertise to manage pain. Nothing in this trial will impede patients them from receiving whatever pain

treatment they and their team agree are appropriate and evidence-based. The benefits to patients include the potential for safer and more guideline-concordant pain management and lower risk of opioid exposure and dependency.

Protection of Human Subjects

Care will be taken to ensure that patients' data are protected. Data from chart review, patient-reported preferences, and patient-reported outcomes will be stored securely on password protected Mayo Clinic research servers within the firewall. Clinicians will still be able to make professional judgments about the appropriateness of engaging patients in specific conversations about pain management throughout their post-surgical recovery and may disregard EHR-prompts as appropriate.

Subject Information

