Exploratory Subaims: We will undertake several exploratory analyses. First, to gain insights into the intervention pathways we will undertake a mediation analysis including only patients randomized to the intervention group. This will employ structural equation models, which will allow us to partition the overall effect of the intervention into direct and indirect effects and compare their magnitude.^{16,17} The results of these analyses will provide information about the relative importance of the mediators on the intervention effect. A second exploratory aim will assess whether there are particular subgroups of patients in which the overall intervention is more effective. Rather than prospectively identify subgroups as in a conventional heterogeneity of treatment effect analysis, we propose to use machine learning tools to cluster intervention patients that respond well or poorly to the intervention. Specifically, we will use a 2/3 random sample of intervention patients to train an unsupervised hierarchical clustering algorithm to identify clusters of patients based on all baseline factors; hierarchical clustering is a machine learning approach that requires no assumptions about numbers of clusters or the relationships between factors, and has been used previously to cluster patients into similar groups.^{18,19} Clusters will then be assessed for relative treatment effectiveness by including cluster indicators in the main models, along with interactions with the intervention indicator. This will allow us to identify clusters which have higher or lower response to the intervention. Finally, we will validate these results using the 1/3 remaining (validation) sample. The results of this aim will provide insights into the types of patients for which the intervention is likely to be most or least effective.

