C.9.viii. Sample size. Our sample size is determined by the number of patients needed to detect a standardized effect of 0.40 between intervention groups, within either the Hispanic or rural subgroup of patients. The choice of 0.40 SD was informed by the 11-point NRS pain score, which we expect to closely align with the BPI. In preliminary analyses using data from the ongoing E2C2 study,²⁰⁻²² we found the standard deviation for the NRS pain score to be 2.7 for Hispanic cancer patients and 2.5 for rural dwelling cancer patients. Thus 0.40 SD corresponds to approximately a 1 point difference in the NRS pain score; 0.40 also conventionally corresponds to a 'medium' effect size.²³ Notably, a 1-point difference on the BPI as well as other 0 to 11 pain NRS has been shown to be a clinically important difference.^{24,25} The sample size needed to detect a standardized effect of 0.40

with a power of $1-b = 90\%$ and an $a = 0.0253$ (Sidak adjusted for 2 comparisons) is 156 per arm or 312 per group. We anticipate that approximately 10% participants will be rural dwelling Hispanics, based on the fact that ~90% of Hispanic cancer survivors treated at the Mayo Clinic Comprehensive Cancer Center are urban dwelling, RUCA 1 and 2, so assume approximately 10% overlap between the two groups. Allowing for a 10% loss to followup, we therefore plan to enroll $312 \times 1.9/(90\% \text{ followup}) = 659$ patients, of whom at least 50% are Hispanic and 50% rural dwelling.. For other outcomes, we assume followup on 593 patients and will have 90% power to detect a smaller standardized effect of 0.3 with an uncorrected $a = 0.05$. The exploratory subaim will be used to generate hypotheses for further work; results will be descriptive, with confidence intervals reported as appropriate.

References

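### The mediation analysis uses intervention-arm patients only, so it cannot split the intervention effect into direct and indirect parts

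*Protocol*

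**What the plan says.** In the Exploratory Subaims paragraph of the protocol's Data Analysis section, the population is fixed first: "we will undertake a mediation analysis including only patients randomized to the intervention group". The next sentence gives the product: the structural equation models will "partition the overall effect of the intervention into direct and indirect effects and compare their magnitude". The paragraph adds that the results will show how much each mediator matters to the intervention effect. It names no exposure other than the intervention.

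The Mediators paragraph under ASCENT Trial Outcomes lists six candidates. Three are PROMIS short forms (self-efficacy, social isolation, informational support), and one is opioid consumption in OMEs from EHR prescriptions. The other two are behavioural: "adherence to behavioral MMPC plan components (logged count data), use of ASCENT e-tools (minutes/week" (the bracket closes there in the protocol). The table of measures shows the PROMIS mediators collected at 0, 3 and 6 months.

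On who is measured, the Consenting section says "This same Outcome Measure survey bundle will be assigned to enrolled participants", with no restriction by arm. The Control Condition section says "Patients randomized to usual care group will be administered trial PROM outcomes". The Sample size section describes the exploratory work as hypothesis-generating, adding that "results will be descriptive, with confidence intervals reported as appropriate".

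**The concern.** The population rule removes the comparison that the stated product needs. The protocol itself treats the intervention effect as a between-arm quantity: the opening paragraph of Data Analysis assesses it through the coefficient of the intervention indicator. In a sample where that indicator is constant, there is no such coefficient and nothing to partition. Structural equation modelling does not supply the missing contrast.

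The risk is a mislabelled result. A regression of pain on self-efficacy among treated patients could be reported as the share of the intervention effect that runs through self-efficacy. That association is not protected by randomisation and says nothing about whether the intervention moved the mediator. The findings are meant to guide further work, so a wrong label could send that work after the wrong mechanism.

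**Working it through.** The protocol gives no figure for this analysis, so there is none to reproduce. The question is one of identification.

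**Model.** With A the randomised arm, M the mediator and Y the outcome:

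- M = i₁ + a·A + e₁
- Y = i₂ + c′·A + b·M + e₂
- indirect effect = a·b; direct effect = c′; total effect = c′ + a·b

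**Rank check.** In the intervention arm A = 1 for everyone, so A duplicates the intercept.

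- Mediator model, columns [1, A]: rank 1 of 2, so a is not estimable.
- Outcome model, columns [1, A, M]: rank 2 of 3, so c′ is not estimable.
- Without a and c′, neither a·b nor c′ + a·b can be formed. Only b is left.
- With both arms the outcome model has rank 3 of 3.

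This settles the point and needs no assumed effect size.

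**Illustration.** Inputs from the Sample size section: 593 patients followed, and a total effect of −0.40, matching the 0.40 SD target. Assumptions: 1:1 allocation (which does not affect identification), unit variances, b = −0.4, one mediator, one time point, 2000 runs.

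| Case | a | c′ | True a·b | True total | Treated-only slope | Two-arm a·b | Two-arm total |
|---|---|---|---|---|---|---|---|
| 0% mediated | 0 | −0.4 | 0 | −0.4 | −0.400 | 0.000 | −0.402 |
| 50% mediated | 0.5 | −0.2 | −0.2 | −0.4 | −0.398 | −0.200 | −0.400 |
| 100% mediated | 1.0 | 0 | −0.4 | −0.4 | −0.401 | −0.402 | −0.399 |
| No effect | 0 | 0 | 0 | 0 | −0.399 | 0.000 | −0.002 |

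The true values follow from the formulas; in the 50% case, 0.5 × (−0.4) = −0.2 and −0.2 + (−0.2) = −0.4. The treated-only analysis cannot tell the four cases apart.

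A second set of assumed values gives the same pattern. With b = −0.5 and (a, c′) = (0, −0.4), (0.4, −0.2) and (0.8, 0), the treated-only slopes were −0.499, −0.501 and −0.499. The two-arm indirect effects were −0.001, −0.201 and −0.400.

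**Limit of the two-arm model.** Suppose the true b is 0, a = 0.5, c′ = −0.4, and an unmeasured factor loads 0.5 on both M and Y. With unit within-arm variance of M, the estimated b tends to 0.5 × 0.5 / 1 = 0.25. The estimated indirect effect is then 0.5 × 0.25 = 0.125, although the truth is 0. The simulated direct effect was −0.527, while the total stayed at −0.403. Randomisation protects the total effect and the arm-to-mediator path, but not the mediator-outcome path.

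**The case against.** The best defence is that the restricted population has a sensible purpose and only the label is wrong. Plan adherence and e-tool minutes vary within the intervention arm, and mediators and pain are measured repeatedly, so engagement and within-arm change can be studied. That is fair, and it is why relabelling is offered as a remedy. It does not rescue the text. The protocol lists adherence and e-tool use as mediators, not as exposures. Within-arm change after entry at a pain score of 5 or more also mixes any intervention effect with regression to the mean.

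The simulation also returns the slope that was put into it. This is correct: the figures illustrate the point and do not measure harm in this trial. The slope is constant across the cases only because b is held fixed and the mediated share is varied through a and c′. If a mediator carried nothing because b = 0, the within-arm slope would be zero, absent confounding. Treated-only data therefore inform one factor of a·b, but cannot rank mediators by their share of the effect.

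That the PROMIS mediators are collected in controls is an inference, since the Consenting section does not itemise the survey bundle. It is a reasonable one, because the table and the follow-up by a blinded assessor carry no arm restriction. Controls also have access to ASCENT materials, so some e-tool use there is possible; the protocol does not say whether it is logged.

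Finally, detailed model specification could be left to an SAP. Here, however, the protocol positively fixes the population. An SAP that follows it inherits the problem, and one that departs from it contradicts the protocol.

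**Conclusion.** The concern holds. As written, the population and the promised product contradict each other, and none of the intervention's total, direct or indirect effects is identified from intervention-arm patients alone. This rests on the rank argument and on the absence of any other named exposure, not on the simulated values.

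The consequence is modest. The analysis is exploratory and descriptive, and the primary and secondary analyses, the alpha and the sample size do not depend on it. It should still be corrected, because exploratory status excuses imprecision but not reporting a quantity that the analysed data cannot contain.

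**What to change.** **Preferred.** Run the mediation model on all randomised patients, with arm as the exposure, for self-efficacy, social isolation and informational support, and for OMEs where EHR capture allows. Adjust for the baseline mediator and baseline BPI; this is good modelling practice, not something identification of the contrast requires. State that the mediator-outcome path assumes no unmeasured confounding. Report plan adherence and e-tool use as associations within the intervention arm only.

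**Alternative.** Keep the intervention-only population, remove the direct/indirect partition and any wording about the intervention effect, and describe the analysis as within-arm associations.

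**Cost.** For the three PROMIS mediators the preferred route takes wording and programming only, provided the survey bundle in both arms contains them, as the protocol indicates. OMEs may also need a sensitivity analysis for missing capture, since the Health care utilization paragraph says "Established patterns suggest that 80% of patients care will occur at an MC facility". The price is that adherence and e-tool use leave the formal decomposition. The alternative costs wording alone.

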- The study plans to conduct a retrospective chart review and ask subjects to complete a questionnaire.
- The study plans to include subjects previously diagnosed with a specific disease and add newly diagnosed subjects in the future.

The study will use data that have been collected under another IRB protocol. Include in the Methods section and enter the IRB number from which the research material will be obtained. *When appropriate, note when subjects have provided consent for future use of their data and/or specimens as described in this protocol.*

Enter one IRB number per line, add more lines as needed

Data Specimens Data & Specimens _____

Data Specimens Data & Specimens _____

Data Specimens Data & Specimens _____

Data Analysis

All methods will be appropriate for a patient-randomized, multi-site study. In addition, because our primary aim is to assess effectiveness in two potentially overlapping subgroups, we will use a Sidak corrected alpha of $\alpha = 0.0253^{15}$ to assess significance. We will summarize patient characteristics by study arm, and report standardized mean differences (SMDs) to assess balance; we will do this for the entire cohort as well as separately for Hispanic and rural patients. Then, to assess the effectiveness of the intervention on the primary and secondary outcomes we will estimate a series of generalized linear models, each estimated separately for Hispanic and rural patients, respectively, with outcome as dependent variable and intervention status indicator. Each model will be specified with a link and distribution appropriate for the outcome, e.g., logit or linear, and include indicators for randomization factors and any characteristics that have $SMD > 0.1$ across groups. By testing whether the coefficient of the intervention status differs from zero we can assess whether the intervention has an impact on the outcome.

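### The 0.40 SD target equals the 1-point clinically important difference only at the rural SD; at the protocol's Hispanic SD it is 1.08 points, and power for 1 point is about 85%

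*Protocol*

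**What the plan says.** Protocol, C.9.viii (Sample size), sets the trial size by the number needed to "detect a standardized effect of 0.40 between intervention groups, within either the Hispanic or rural subgroup of patients". With 90% power and a Sidak alpha of 0.0253 it arrives at 156 per arm, 312 per subgroup, and uses that number for both subgroups.

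The same paragraph explains the choice of 0.40. From the E2C2 study, "we found the standard deviation for the NRS pain score to be 2.7 for Hispanic cancer patients and 2.5 for rural dwelling cancer patients". It continues: "Thus 0.40 SD corresponds to approximately a 1 point difference in the NRS pain score". It then adds that "a 1-point difference on the BPI as well as other 0 to 11 pain NRS has been shown to be a clinically important difference".

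Under Data Analysis, the primary aim is effectiveness in the two subgroups. Each is modelled separately and each is assessed at 0.0253 by "testing whether the coefficient of the intervention status differs from zero".

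**The concern.** The clinical case for the sample size runs from 0.40 SD to 1 point to clinical importance. One conversion is used for two subgroups with different standard deviations. A fixed number per arm gives both subgroups equal power for a standardized effect, but not for a difference in points, and it is the difference in points that the protocol calls important.

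The Hispanic comparison is one of two primary tests and has to stand on its own power. A reader could take the paragraph to mean that a 1-point benefit has the same 90% chance of detection in each group. If the rural result were significant and the Hispanic result not, that reader might conclude that Hispanic patients gain nothing clinically important, when part of the contrast could reflect lower power.

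**Working it through.** **Inputs.** All are from C.9.viii except sidedness: alpha 0.0253; power 90%; effect 0.40 SD; 156 evaluable per arm, equal arms; NRS SD 2.5 (rural) and 2.7 (Hispanic); clinically important difference 1 point. The paragraph does not state sidedness. The test against zero under Data Analysis implies two-sided, and a one-sided calculation gives 131 per arm, which does not match.

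**Step 1: alpha.** 1 − (1 − 0.05)^0.5 = 0.0253. This reproduces.

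**Step 2: the protocol's sample size.** n per arm = 2(z₁₋α/₂ + z₁₋β)²/d² = 2(2.237 + 1.282)²/0.40² = 154.7, so 155 by the normal approximation. The t-test solution is 156.0. The stated 156 reproduces, and its power at 0.40 SD is 90.0% (t-test) or 90.2% (normal).

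**Step 3: 0.40 SD in points.** Rural: 0.40 × 2.5 = 1.00. Hispanic: 0.40 × 2.7 = 1.08.

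**Step 4: power for 1 point at 156 per arm.** The normal approximation is Φ[(1/SD)·√(156/2) − 2.237].

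| Group | SD | 1 point in SD units | Power, normal | Power, t-test | n per arm for 90% (t-test) |
|---|---|---|---|---|---|
| Rural | 2.5 | 0.400 | 90.2% | 90.0% | 156 |
| Hispanic | 2.7 | 0.370 | 84.9% | 84.6% | 182 |

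The chance of missing a true 1-point benefit in Hispanic patients is therefore about 15%, against 10% in rural patients.

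**Step 5: sensitivity to the SD.** The SD of the outcome in enrolled patients is not in the protocol. For assumed values, power for 1 point (t-test) is 96% at SD 2.2, 90% at 2.5, 87% at 2.6 and 85% at 2.7.

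**Step 6: step-down testing.** Test the smaller p-value at 0.0253 and, if it is significant, the other at 0.05. At 0.05, Hispanic power for 1 point is Φ(3.271 − 1.960) = 90.5%. If the two tests were independent, Hispanic power would be its power at 0.0253 plus (rural power) × (gain from moving to 0.05):
- rural effect 0.40 SD: 0.849 + 0.902 × (0.905 − 0.849) ≈ 0.90;
- no rural effect: 0.849 + 0.0253 × (0.905 − 0.849) ≈ 0.85.

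A simulation with an assumed correlation of 0.10 between the tests gives 0.850 rising to 0.899 in the first case and about 0.851 in the second. With no effect in either group, the chance of any rejection is 1 − (1 − 0.0253)² = 5% under independence (simulated 0.050 at correlation 0.10).

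**The case against.** A reader might infer that the sample size is miscalculated, or that the protocol promises 90% power for 1 point and delivers 85%. The document supports neither. It attaches 90% to 0.40 SD, and 156 per arm is right for that. It calls the conversion approximate, gives both standard deviations in the preceding sentence, and 1.08 does round to 1.

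Nor does it follow that the Hispanic comparison is underpowered in fact:

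- The standard deviations are for the NRS in another study. The primary outcome is the BPI SF, which the protocol only expects to behave similarly, and enrolment is restricted to NRS 5 or more. The relevant SD could be smaller.
- The 85% is for an unadjusted comparison at one time. The protocol plans covariates, and mixed models for repeated outcomes. A covariate correlated 0.3 to 0.5 with the outcome (assumed) reduces the SD to 2.7 × √(1 − r²) and gives about 88% to 94%. Averaging two follow-ups correlated 0.7 (also assumed) gives an SD of 2.7 × √0.85 = 2.49 and about 90%.

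These points stand, and they limit the finding to the link between 0.40 SD and 1 point in one subgroup. They do not remove it. The protocol's own calculation takes no credit for adjustment or repeated measures and gives no correlation, and 2.7 is the only Hispanic SD it offers. An 8% rounding of the effect costs about 5 percentage points of power, or 26 patients per arm (182 − 156), and the text does not say so.

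**Conclusion.** The point holds in limited form. The number per arm is correct for 0.40 SD, but the 1-point justification carries 90% power only at the rural SD. On the protocol's own figures the Hispanic difference detectable with 90% power is 1.08 points, and power for 1 point is about 85%. This assumes 156 evaluable Hispanic patients per arm, an SD of 2.7 carrying over to the BPI, and an unadjusted two-sample t-test. A smaller SD, covariate adjustment or repeated measures could close the gap. The shortfall is modest. It deserves correction because it concerns a primary test and because the remedy needs no further patients.

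**What to change.** 1. In C.9.viii, give the difference detectable with 90% power by group, 1.00 point rural and 1.08 points Hispanic, and state about 85% power for 1 point in Hispanic patients. Add that these rest on NRS standard deviations and an unadjusted comparison. This costs a sentence or two and makes one implied figure slightly less favourable.

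2. Under Data Analysis, replace the single-step Sidak rule with its step-down (Holm-Sidak) version: the smaller p-value is tested at 0.0253 and, if significant, the other at 0.05. Familywise error stays at 5%, and Hispanic power for 1 point rises to about 90% if the rural effect is 0.40 SD. There is almost no gain if the rural effect is absent. The small downside is that simultaneous confidence intervals matching the step-down test are less simple than under the single-step rule.

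3. Read a non-significant Hispanic result through its confidence interval against 1 point, not as evidence of no important effect.

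No change to enrolment is proposed.

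### The 90% power claimed for a 0.3 SD effect on the other outcomes assumes all 593 patients in one analysis at alpha 0.05, but the planned models are fitted in subgroups of 312, where power is about 66–75%

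*Protocol*

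**What the plan says.** The Data Analysis section of the protocol defines the effectiveness analysis for primary and secondary outcomes alike: "we will estimate a series of generalized linear models, each estimated separately for Hispanic and rural patients, respectively". Secondary outcomes are named there, so the separate-subgroup structure covers them. The same section says of significance testing that "we will use a Sidak corrected alpha of" 0.0253. The reason given is that the primary aim concerns two overlapping subgroups, but the section states no other alpha for secondary outcomes.

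Section C.9.viii (Sample size) first sizes each subgroup at 156 per arm, 312 in total, for 0.40 SD at alpha 0.0253 with 90% power. It then turns to the remaining outcomes: "For other outcomes, we assume followup on 593 patients and will have 90% power to detect a smaller standardized effect of 0.3". The alpha it gives for these is 0.05, without the Sidak correction.

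The protocol's only reference to the entire cohort in the statistical text is for the baseline summaries and balance statistics. The mixed-model and imputation text adds no pooled population, and the exploratory cluster analysis reuses the main models.

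**The concern.** The two sections disagree on which patients enter the secondary analyses (312 per subgroup or 593 pooled) and on the alpha applied (0.0253 or 0.05). A power figure describes a particular analysis, and this one describes a pooled comparison that the analysis section does not include.

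The secondary outcomes include physical function, which the Hypothesis section places beside pain as something the intervention will improve. If the trial is analysed as written, a reader who trusts the 90% figure will take a null secondary result as stronger evidence of no effect than it is. The conflict also leaves open, after the data are seen, whether to use pooled or subgroup models and 0.05 or 0.0253, with support in the protocol for either.

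**Working it through.** **Inputs**
- Evaluable patients per subgroup: 312, i.e. 156 per arm (C.9.viii). This implies 1:1 allocation.
- Followed cohort: 593 (C.9.viii), i.e. 296.5 per arm at 1:1.
- Effect for other outcomes: d = 0.3 SD. Alpha: 0.05 (C.9.viii) or 0.0253 (Data Analysis). Sidedness is not stated; two-sided is assumed.

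**Where 593 comes from.** 312 × 1.9 = 592.8. Dividing by 0.9 gives 658.7, so 659 are enrolled, and 659 × 0.9 = 593.1. It is therefore the union of both subgroups after dropout.

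**Formulas (normal approximation, n per arm)**
- Power = Φ(d·√(n/2) − z₁₋α/₂)
- Effect detectable with 90% power = (z₁₋α/₂ + 1.2816)·√(2/n)
- z₁₋α/₂ = 1.960 at 0.05 and 2.237 at 0.0253

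Each result was checked with the noncentral t distribution.

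**Primary sizing reproduced.** The Sidak alpha is 1 − 0.95^½ = 0.0253. For d = 0.40, alpha 0.0253 and 90% power, the t test needs 155.99, i.e. 156 per arm, as the protocol states. The same method can therefore be applied like for like to the other outcomes.

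**The stated figure, on its own pooled inputs.** 0.3 × √(296.5/2) = 3.653, and Φ(3.653 − 1.960) = 95.5% (t test 95.4%). The effect detectable with 90% power is 3.2415 × √(2/296.5) = 0.266 SD (t test 0.267). The stated pair of 90% and 0.3 SD is probably 0.27 rounded up, which is conservative for a pooled test.

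**The analysis as written.** 0.3 × √(156/2) = 2.650.
- At 0.05: Φ(2.650 − 1.960) = 75.5%
- At 0.0253: Φ(2.650 − 2.237) = 66.0%
- Detectable effect at 0.05: 3.2415 × √(2/156) = 0.367 SD
- Detectable effect at 0.0253: (2.237 + 1.2816) × √(2/156) = 0.398 SD

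| Analysed set | Alpha | Power for 0.3 SD (t test) | Effect detectable with 90% power (t test) |
|---|---|---|---|
| 593 pooled | 0.05 | 95.4% | 0.267 SD |
| 593 pooled | 0.0253 | 92.0% | 0.290 SD |
| 312, one subgroup | 0.05 | 75.2% | 0.368 SD |
| 312, one subgroup | 0.0253 | 65.6% | 0.400 SD |

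**Size needed.** By the t test, 90% power for 0.3 SD takes 235 per arm at 0.05, or 277 per arm at 0.0253, in each analysed set. The plan has 156 per arm.

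**The case against.** 1. **The sentence is true for a pooled comparison.** On 593 patients at 0.05 it is correct and even cautious, so this is not a slip of calculation. That stands: the fault is a mismatch between two sections. The mention of 593 patients may well show that a pooled analysis was intended. If so, the Data Analysis section is the one to change, because it says the opposite for secondary outcomes. An unseen SAP could add a pooled model, but the protocol's two statements would still conflict.

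2. **The alpha conflict can be read away.** The Sidak correction is justified by the primary aim, and C.9.viii expressly uses 0.05 for other outcomes. On that reading 75% is the relevant figure and 66% falls away. This is a reasonable reading, though the Data Analysis section does not say it. Even then, 75% is well short of 90%.

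3. **Covariates and repeated measures would raise power.** The models adjust for randomization factors and imbalanced characteristics, and repeatedly collected outcomes get mixed models. Suppose baseline is adjusted for, with a correlation r of 0.3 to 0.5 between measurements. For a single follow-up the residual variance is 1 − r² (0.91 to 0.75), and power at 0.05 becomes 79–86%. For an effect averaged over 3 and 6 months, with equal correlations and a constant effect, the variance is (1 + r)/2 − r² (0.56 to 0.50), and power is 94–96%. The gain is real but rests on assumed values. The protocol gives no correlation, does not say that the target is the average over visits, and uses no such gain in its own sizing. The stated 90% therefore cannot be credited to it.

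4. **Other outcomes is undefined.** It may also cover measures such as utilization. The contradiction is firm only for the secondary outcomes, which the Data Analysis section names.

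**Conclusion.** The concern holds. The power statement in C.9.viii does not describe the secondary analyses set out in the Data Analysis section. A true 0.3 SD effect would be missed in about 25% of subgroup tests at 0.05, or 34% at 0.0253, instead of 10%.

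These figures assume 1:1 allocation, 312 evaluable patients per subgroup, and a two-sided unadjusted comparison at one time point, which is the basis the protocol itself uses for the primary outcome. If each subgroup held only half of 593, power would be 73% or 63%. The primary sizing, the enrolment target and the error control for the primary outcome are unaffected.

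**What to change.** Reconcile the two sections in one of two ways.

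- **Keep the separate subgroup models** and replace the sentence in C.9.viii with what they deliver: within each subgroup of 312, 90% power for 0.37 SD at alpha 0.05 (0.40 SD at 0.0253), and power for 0.3 SD of 75% (66%).
- **Or state in the Data Analysis section** that secondary outcomes are tested in one pooled model of all randomised patients, with 90% power for 0.27 SD at 0.05, and report the subgroup estimates alongside.

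In either case, give a single alpha for secondary outcomes, the same in both sections, and say which outcomes the power statement covers. If gains from baseline adjustment or repeated measures are to be counted, state the assumed correlation and the target time point or average.

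The cost is wording only: a less favourable figure in the first case, one added model in the second. No extra patients are needed. The choice should be fixed before outcome data are examined by arm.
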